#### Open-Label Period (Treatment Cycles 2-4)

For a given subject, the Dysport dose for treatment cycles 2, 3 and 4 will be based on the investigator's judgement (based on efficacy and safety).

- Treatment cycle 2: the Dysport dose can either be the Dysport dose assessed in the previous treatment cycle (double-blind period) for the current cohort or the Dysport dose of the following cohort (provided it has been approved by the DRC).

- Treatment cycles 3 and 4: the Dysport dose can either be the dose assessed in the previous treatment cycle, a lower dose or the dose of the following cohort (provided it has been approved by the DRC).

If any subject fulfils the retreatment criteria and needs a higher dose for treatment prior to the DRC having approved the next dose level, the subject can either accept the dose level currently on, or delay injection until the next dose level is approved by the DRC or withdraw from the study.

A subject can receive up to a maximum of 4 treatment cycles with Dysport. The last treatment cycle should last at least 12 weeks and should not be initiated after Week 36.

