### 3.7.3 *Retreatment Criteria (Stage 1 and Stage 2)*

From Week 12 onwards (Stages 1 and 2), need for retreatment will be assessed at each visit. All subjects willing to continue in the study will be offered to receive Dysport (under an open-label design).

Retreatment with Dysport will only be initiated if all of the following criteria are fulfilled (retreatment criteria):

- At least 12 weeks have elapsed since the last treatment received.
- Based on investigator's judgement, this is in the best interest of the subject.
- Subject is willing to be retreated.
- The subject has not experienced any unacceptable AE as judged by the investigator.
- Negative urine pregnancy test.
- Negative drug screen test for illicit drugs.

Details on dose administration for Stage 1 are provided in Sections [3.7.2.1](#) and for Stage 2 in Section [3.7.2.2](#).

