- a From Week 12 onwards, if no retreatment is required, the subject will attend Additional Visits every 6 weeks until retreatment is required or Week 36 (EOS) is reached. When subject is eligible and all retreatment criteria are fulfilled at any visit, the subject will complete all the assessments planned at this visit, all assessments planned at End of Cycle 1 (if not already performed at the visit) and will enter Cycle 2 Day 1 (which will be on the same day as End of Cycle 1).
- b This visit (Week 36) is the End of Study if the subject is still not eligible for retreatment at the End of Cycle 1.
- c ICF to be signed prior to any screening assessment.
- d To be performed only if this visit is the End of Study or Early Withdrawal.
- e To be assessed at Screening Visit, then 1 week prior to the next planned visit and at the visit. PGI-C will be assessed Week 6 onwards only.
- f To be assessed at the site during the visit.
- g To be assessed at Screening Visit, then 2 weeks prior and 1 week prior to the next planned visit and at the visit.
- h To be assessed at Screening Visit, and then from 2 weeks prior to the next planned visit, subjects need to record daily if they had intercourse, the number of intercourse instances, corresponding pain during each intercourse instance on an 11-point NRS, and details of pain rescue medication if taken to prevent or treat vestibular pain.

Study Procedures and Assessments	Pretreatment		Double-Blind Treatment Period Cycle 1							End of Cycle 1/ EOS or EWD [b]	
	V1	V2	V3	V4	V5 [a]	Additional Visits [a]					
						V6	V7	V8			
Visit Day/Week No.	Screening (Day -14) [m]	Baseline (Day 1)	Week 2 (Day 15)	Week 6 (Day 43)	Week 12 (Day 85)	Week 18 (Day 127)	Week 24 (Day 169)	Week 30 (Day 211)	Week 36 (Day 253)		
Type of visit	Clinic	Clinic	Telephone	Clinic	Clinic	Clinic	Clinic	Clinic	Clinic		
Visit Window	-14 days/ +3 days			±3 days	±5 days	+14 days	±14 days	±14 days	±14 days	±14 days	

i FSH only at Screening Visit.

j Performed after all the other procedures and assessments. Subjects to remain at the clinic for at least 30 minutes after the study drug administration.

k To be assessed weekly from 2 weeks prior to the next planned visit (assessment on the day of the visit should be avoided). Subjects need to rate the level of the corresponding pain following insertion of vaginal dilator (number 6 size) on an 11-point NRS and record details of associated pain medication if consumed.

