3 STATISTICAL METHODS

3.1 Statistical analysis strategy

The statistical analyses will be performed in accordance with the ICH E9 guideline and will be based on the pooled data from the individual study sites, unless otherwise stated.

Medpace will perform the statistical analysis of the efficacy, safety, and antibodies data.

Overall, the analysis strategy is to evaluate safety and efficacy of Dysport compared to Placebo after single administration (DB period), and to evaluate efficacy and safety over repeated Dysport treatments, using analyses by Active Treatment Cycle.

Listings will be presented by subject for DB and OL periods together while the tables associated with the DB period will be separated from the tables assessing repeat treatment with Dysport.

Only descriptive statistics of Stage 1 data will be provided.

Double-Blind Period (Stage 1 Cycle 1) Analyses

For the analysis of the DB period, tables will be displayed using the following treatment group (DB treatment group) labels, in the following order:

- Placebo: placebo groups from all cohorts will be pooled, including for mVPAQ pain, mVPAQ life interference and mFSFI pain domain of cohort 1 despite the change in recall period and time of assessments (see protocol version 3.0).
- Dysport
 - Groups by dose (Dysport 100U, 300U, 400U, 500U, etc.)
 - All Dysport

[figure not shown]
Note: Cohort 1 (100U), 2 (300U), 3 (400U) and 5 (500U) included PVD2 subjects only. Cohort 4 (400U) and 6 (500U) included PVD1 subjects only.

Repeat treatment: Active Treatment Analyses

To assess efficacy and safety data over repeat treatments, data will be analysed using the Active Treatment Cycle approach as described in [Figure 1](#) below. These analyses will be performed on the Active Treatment population:

- for subjects treated with Dysport in the DB period, the first cycle in the DB period will be the first Active Treatment Cycle.
- for subjects treated with placebo in the DB period, the first cycle in the OL period will be the first Active Treatment Cycle.

[Figure 1](#) Active Treatment Cycle Analysis

Three types of summary tables will be produced:

- Summary by number of active treatment cycles: these tables will present the long-term efficacy and safety data with all doses combined, and will display subjects with at least 1 (2, 3 and 4) active treatment cycles.
- Summary by dose received at each active treatment cycle: to evaluate the safety of each dose at a given cycle.

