- Description of the actual dose received in each cycle by DB treatment group and overall subjects from the safety population.
The number and percentage of subjects receiving the actual dose will be provided.
- Description of the actual dose at each active treatment cycle, by treatment received for the active treatment cycle and overall subjects from the safety population.
The number and percentage of subjects receiving the actual dose will be provided for each active cycle.
- A listing of exposure data will also be provided.

3.9.2 *Adverse events*

Adverse events will be coded using the Medical Dictionary for Regulatory Activities (MedDRA) latest version (23.0 or later) and presented by MedDRA preferred term and system organ class.

AEs will be classified as treatment-emergent AEs (TEAEs) according to the rules below:

- Events with start date (and time) on or after the date (and time) of first IMP administration.
- Events whose severity worsens on or after the date (and time) of first IMP administration.

A TEAE that occurs under a particular treatment cycle and worsens in intensity under a different treatment cycle will be considered as treatment emergent under the two treatment cycles. In the event of another occurrence of a TEAE with a change in intensity under a different treatment cycle, the subject will also be counted in that different treatment cycle. A given AE will be assigned to the dose received prior to the onset of the AE in the designated treatment cycle.

An overall summary table of all adverse events will be presented (as described in Section 3.9) and include the following:

- Subjects with any TEAEs,
- Subjects with any TEAEs by maximum intensity,
- Subjects with any TEAEs related to IMP,
- Subjects with any TEAEs related to IMP by maximum intensity,
- Subjects with any TEAEs leading to drug withdrawal,
- Subjects with any SAEs,

- Subjects with any TEAEs leading to death,
- Subjects with any SAEs related to IMP,
- Subjects with any TEAEs of special interest (AESIs).

This summary table will be also be provided by dose received at each active treatment cycle.

All TEAEs will be summarized with the number and percentage of subjects with adverse events classified by primary system organ class and preferred term. The number of occurrences of a TEAE will also be presented. This summary table will also be provided by dose received at each active treatment cycle.

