3.12 Rules and data formats

Data will be presented using an appropriate number of decimal places (i.e. the number of decimal places used does not imply undue precision). Raw data will be presented to the number of decimal places collected, and derived data will be presented to an appropriate number of decimal places. The appropriate number of decimal places will be determined by general practice, mathematical rationale or scientific rationale (e.g. age should be presented in whole numbers).

Mean, median, standard deviation and standard errors of the mean (SE) values will be reported to one decimal place greater than the raw/derived data that they summarize. Minimum and maximum values will be reported with the same precision as the raw data.

Percentages will be reported to one decimal place and 0% will not be presented. Percentages will be calculated using a denominator of all subjects in a specified population. The denominator will be specified in a footnote to the tables for clarification if necessary.

Percentiles (e.g., 25%, 75%) should be presented to one decimal place more than the raw/derived data.

Lower and upper confidence interval values should be presented to one decimal place more than the raw/derived data (i.e., to the same number of decimal places as the mean).

P-values will be reported to four decimal places (e.g.: $p=0.0037$), after rounding. P-values which are less than 0.0001 will be presented as ‘<0.0001’.

All values below or above a limit of detection (e.g. <0.1 or >100) will be listed as such.

All text fields must be left justified and numeric or numeric with some text specification (e.g.: not done, unknown, <4.5, ...) must be decimal justified. Dates will be presented in the format [ddmmmyyyy] and times in the format [hh:mm].

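### Adverse events are tabulated as crude percentages over cycles of unequal length with no common time window, which can distort comparisons between arms, doses and cycles in either direction

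*SAP*

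**What the plan says.** On the AE summaries, SAP 3.9.2 plans: "All TEAEs will be summarized with the number and percentage of subjects with adverse events classified by primary system organ class and preferred term". It adds: "The number of occurrences of a TEAE will also be presented". The tables are given by double-blind group for cycle 1 and by number of active cycles, and further: "This summary table will also be provided by dose received at each active treatment cycle". SAP 3.1 gives the purpose of that last layout: "Summary by dose received at each active treatment cycle: to evaluate the safety of each dose at a given cycle". On denominators, SAP 3.12 says: "Percentages will be calculated using a denominator of all subjects in a specified population". SAP 3.9.1 derives the duration of each cycle and describes it by cycle and dose, but no AE table uses it.

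On cycle length, protocol 3.7.3 requires before retreatment: "At least 12 weeks have elapsed since the last treatment received". It also requires investigator judgement, the subject's willingness and no unacceptable AE so far. A woman who is not retreated in cycle 1 attends "Additional Visits every 6 weeks until retreatment is required or Week 36 (EOS) is reached" (Table 2, footnote a). For the open-label cycles, protocol 3.7.2 says: "The last treatment cycle should last at least 12 weeks and should not be initiated after Week 36". Retreatment can also wait for the DRC to confirm a dose (Table 3, footnote a) or for onsite visits to resume (5.2.2.4). After the early termination, SAP 1.3.5 has subjects followed to 12 weeks after their last dose.

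On the primary safety window, protocol 3.2.1 defines the Stage 1 primary endpoint over a fixed period, Baseline to Cycle 1-Week 6. SAP 3.9 plans no AE table for that period, and the list of protocol changes in SAP Section 5 does not mention it.

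**The concern.** A crude percentage of subjects with an event depends on how long they were watched as well as on their risk. Here the length of observation is set by when a woman is retreated, by DRC and COVID-19 delays, by the Week 36 limit on starting a cycle, and by early closure. Two cells of the same table can therefore differ because follow-up differed.

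The safety of increasing doses is the primary Stage 1 objective, and safety over repeat treatment is a stated aim of SAP 3.1. Both are read from these percentages. Early closure adds a possible link between dose and follow-up: the last cohorts received the highest doses and are the likeliest to have been cut short, although the documents do not say how many were. Each dose group is also set beside placebo pooled over all cohorts, so follow-up differences between cohorts enter that comparison too.

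**Working it through.** **Inputs from the documents.** Visit days in protocol Tables 2 and 3; at least 12 weeks between treatments (3.7.3); visits every 6 weeks after that; no cycle started after Week 36 (3.7.2).

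**Assumptions, not in the documents.** A constant hazard giving a proportion p of subjects with an event per 12 weeks, and a probability q of retreatment at each eligible visit.

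**Step 1: cycle lengths.** Weeks = (visit day − 1)/7.
- Cycle 1: (85 − 1)/7 = 12 at the earliest retreatment and (253 − 1)/7 = 36 at the latest. This reproduces the protocol's Week 12 and Week 36.
- The last possible visit is (337 − 1)/7 = 48 = 36 + 12.
- Cycle 2 begun at Week 12 and ending at Week 36 (5.2.3.5): 24 weeks. Begun at Week 36: 12 weeks.
- Cycle 3 cannot begin before Week 24: 12 weeks to Week 36, or 18 if the further visit in 5.2.3.4 takes place at Week 42.
- Cycle 4 cannot begin before Week 36: about 12 weeks.

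Visit windows and early withdrawal widen these ranges both ways.

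**Step 2: effect of length alone.** Crude % = 1 − (1 − p)^(L/12).

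| p per 12 weeks | L = 12 | L = 18 | L = 24 | L = 30 | L = 36 |
|---|---|---|---|---|---|
| 10% | 10.0 | 14.6 | 19.0 | 23.2 | 27.1 |
| 20% | 20.0 | 28.4 | 36.0 | 42.8 | 48.8 |
| 30% | 30.0 | 41.4 | 51.0 | 59.0 | 65.7 |
| 40% | 40.0 | 53.5 | 64.0 | 72.1 | 78.4 |

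**Step 3: realistic mixtures of lengths, p = 30%, q = 0.5.** An unretreated cycle is taken to end at Week 36, or at 12 weeks if that is later.
- Cycle 1 lasts 12, 18, 24, 30 or 36 weeks with probability 0.5, 0.25, 0.125, 0.0625 and 0.0625. Crude % = 0.5×30.0 + 0.25×41.4 + 0.125×51.0 + 0.0625×59.0 + 0.0625×65.7 = 39.5.
- Cycle 2 begun at Week 12 (0.5 of all subjects): 0.5×30.0 + 0.25×41.4 + 0.25×51.0 = 38.1. Begun at Week 18 (0.25): 0.5×30.0 + 0.5×41.4 = 35.7. Begun at Week 24, 30 or 36 (0.21875 in total): 30.0. Weighted over the 0.96875 who enter cycle 2: about 35.7.
- Cycles 3 and 4 last 12 weeks under this rule: 30.0.

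A simulation of 200,000 subjects on this schedule agrees and gives the other values of q. Departures from 30.0 in cycles 3 and 4 are simulation error.

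| q per visit | Mean cycle 1 length, weeks | Crude %, cycles 1 / 2 / 3 / 4 |
|---|---|---|
| 1.0 | 12.0 | 30.0 / 30.0 / 30.0 / 30.1 |
| 0.7 | 14.6 | 34.6 / 33.7 / 30.1 / 30.1 |
| 0.5 | 17.6 | 39.5 / 35.7 / 30.1 / 29.7 |
| 0.3 | 22.6 | 46.9 / 36.6 / 29.9 / 30.0 |

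A cycle 3 running to 18 weeks would lessen the fall.

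**Step 4: Dysport against placebo in cycle 1, same hazard.** With q = 0.3 on Dysport and 0.7 on placebo, the table shows 46.9% against 34.6%. With equal q there is no difference. With the two values exchanged, the contrast reverses.

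**Step 5: candidate remedies.** Counting onsets within 12 weeks of injection returns about 30% in every cycle and for every q. A first-event rate is also stable under constant hazard, at about 2.9 to 3.0 per 100 subject-weeks. If instead 30% of subjects have an event only in the first weeks, the rate is about 30/12 = 2.5, 30/24 = 1.25 and 30/36 = 0.83 per 100 subject-weeks, so a long cycle would look safer for no reason.

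**The case against.** The case for leaving the tables alone has weight.
- The analysis is descriptive only (SAP 3.1.2).
- Cycle durations are tabulated, AE listings carry start dates, and treatment cycle day is derived (SAP 3.11), so a careful reader can see that follow-up differs.
- Protocol 8.1.4 says toxin-spread symptoms arise hours to weeks after injection, so a longer cycle adds few of them. SAP 3.9.2 also removes candidate AESIs whose timing does not fit the mechanism.
- Planned Dysport cells in cohorts 1 to 6 are small: 8, 8, 14 and 16 at 100, 300, 400 and 500 U. The 9.4-point gap between cycles 1 and 3 at q = 0.5 is 0.094×8 = 0.75 to 0.094×16 = 1.5 women.
- A woman reaching cycle 4 must have had three earlier cycles of about 12 weeks each. Much of any fall by cycle is therefore a change in who is in the table.

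These points limit the size of the problem and confine it mainly to background events. They do not remove it. The percentages are the reported safety result, and a separate duration table does not let a reader recount events within a common window.

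A reader might infer more than the documents support:
- **That repeat dosing will look safer with every cycle.** There is no fall if everyone is retreated at Week 12, and none from cycle 3 to 4 under any q tried.
- **That lasting responders will make Dysport look worse than placebo.** Protocol 3.7.3 sets no response threshold. Judgement, DRC timing and COVID-19 delays also govern retreatment, so the direction is not fixed.
- **That an unchanged risk will print as 66% against 30%.** That compares a cycle in which every woman lasts 36 weeks with one in which every woman lasts 12.

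**Conclusion.** The concern holds in a conditional form. The SAP reports crude percentages over cycles of unequal length, and no AE table uses a common window. The protocol's own primary Stage 1 window has no table, and this is not declared as a change. Comparisons between arms, doses and cycles can be distorted in either direction, mainly for background AEs.

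The size depends on assumptions. At 30% per 12 weeks and q = 0.5, an unchanged risk prints as about 40/36/30/30% over cycles 1 to 4. Across the q values tried, the distortion in cycle 1 runs from none to about 17 points (46.9 − 30.0). The hazard and the retreatment probabilities are assumed; only the range of lengths comes from the protocol. Actual lengths after early closure are not given. Selection into later cycles of women without an unacceptable AE is a separate effect that no exposure adjustment removes.

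**What to change.** In SAP 3.9.2, for the TEAE, SAE and AESI tables that compare arms, doses or cycles:
1. Add a cycle 1 table of onsets from Baseline to Week 6, the protocol's primary Stage 1 window.
2. Add tables of onsets within 12 weeks of each cycle's injection, with subjects injected in that cycle as denominator. Twelve weeks matches the minimum retreatment interval and the follow-up after closure, so it should be nearly complete apart from withdrawals.
3. Keep the whole-cycle counts as supportive, with cycle duration shown beside them.
4. Give person-time rates only as supportive, with a note that they understate early-onset events in long cycles.
5. Footnote that later cycles contain only women without an unacceptable AE so far.

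If the Week 6 table is not added, SAP Section 5 should record its omission as a change from protocol.

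The cost is SAP wording and a few extra tables from dates already collected. The drawback is that late-onset events appear only in the supportive tables.

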Summary tables will also be presented by SOC and PT for SAEs, TEAEs by intensity, TEAEs by causality, and non-serious TEAEs with at least 2 subjects. TEAEs will also be summarized by decreasing overall PT frequency

If the intensity or causality is missing for a TEAE, it will be considered as missing in the summary tables. In the event of multiple TEAE being reported by the same subject within the same SOC/PT, the maximum intensity (severe > moderate > mild > missing) and the most serious causality (related > not related > missing) will be chosen.

Listings will be presented and sorted by DB treatment group, subject ID, start date of AE, primary system organ class, preferred term and verbatim text for all adverse events recorded during the study. Other information collected, such as end date and outcome of AE, will be provided in the listings.

Listings of SAE, adverse events leading to discontinuation from the study, clinically significant events, adverse events leading to drug withdrawal and death will also be presented.

TEAEs will be identified in the adverse events listings. Pre-treatment AEs and clinically significant AEs will also be flagged in the AE listings.

Adverse Events of Special Interest (AESIs)

Adverse events of special interest (AESIs) for Dysport in this study are defined as:

- Any TEAE that suggests a possible remote spread of effect of the toxin, or
- Any TEAE related to urinary incontinence or faecal incontinence, or
- Any TEAE assessed as a potential hypersensitivity reaction,

where there is a reasonable possibility of causal relationship with treatment with Dysport, regardless of the investigator reported causality.

The method described below is used for identification and analysis of events that may be qualified as TEAEs that suggest a possible remote spread of effect of the toxin, events related to incontinence or faecal incontinence or events suggestive of hypersensitivity like reactions.

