TEAEs due to possible remote spread of the effects of Dysport will be identified using the list of MedDRA preferred terms (PTs) compatible with the mechanism of action of BTX-A and based on the recommendations from the Committee for Medicinal Products for Human Use (CHMP) and the Food and Drug Administration (FDA). TEAEs potentially representing hypersensitivity reactions will be identified using the Standardised MedDRA Query (SMQ) (narrow search query) for hypersensitivity reactions. TEAEs that are possibly related to urinary incontinence or faecal incontinence will also be identified using the list of MedDRA preferred terms.

The list of MedDRA preferred terms used to identify any potential AESI is provided in *AESIs MeDDra.xlsx*.

All TEAEs identified using the search strategy described above will be medically evaluated during the study before the database lock and unblinding, by the sponsor to identify events which could possibly represent “remote spread of effect of toxin”, or which are suggestive of “related to urinary incontinence or faecal incontinence” or “hypersensitivity reactions” due to study treatment administration. Events will be disregarded as an AESI if they are confounded by the presence of alternative clinical aetiologies (medical history, concomitant medication or diagnosis which could account for the symptoms); if they are considered to be local effects instead of distant spread, as judged by the site of injection; the time period between the last study treatment administration and event onset is not in accordance with the expected mechanism of action; or due to insufficient information/evidence to make an assessment.

In the summary data tabulations and listings, only the final list of AESIs confirmed by the sponsor as “a possible remote spread event”, “hypersensitivity reactions” or “urinary incontinence and faecal incontinence” will be taken into account.

Besides the AESI listing, a summary table of AESI will be presented by SOC and PT (as described in Section 3.9) and include the following:

- Subjects with any AESI suggesting a possible remote spread of effect of the toxin,
- Subjects with any AESI related to urinary incontinence or faecal incontinence,
- Subjects with any AESI assessed as a potential hypersensitivity reaction.

3.9.3 ***Laboratory data***

All laboratory data will be presented in the units of International System of Units (SI).

The following summaries will be provided:

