3.10.2 Missing or incomplete dates

In all listings, missing or incomplete dates should be left as they have been recorded. However, for calculation / sorting / assignation based on dates, the following methods will be used:

The most conservative approach will be systematically considered (i.e. if the onset date of an AE/concomitant medication is missing / incomplete, it is assumed to have occurred during the study treatment phase (i.e. a TEAE for AEs) except if the partial onset date or other data [stop date, ...] indicates differently).

- A missing/incomplete date of medical history or disease diagnosis will be assumed to have occurred before any study treatment,
- A medication with partial start and stop dates will be considered as concomitant treatment, except if the partial dates indicate differently,
- If an AE or SAE onset date is partial or missing, the event will be allocated to the first treatment where onset could have occurred (taking into account date and time stopped),
- If the start date of a medication is partial or missing, the medication will be assigned to the most recent treatment received on or before the medication start date (taking into account date stopped).

Where this is possible, the derivations based on a partial date will be presented as superior inequalities (i.e.: for an AE started in FEB2004 after the administration performed on 31JAN2004, the days since last dose will be “ ≥ 2 ”, similarly the duration of ongoing AEs or medication will be “ $\geq xx$ ” according to the start and last visit dates).

If the date of diagnosis for provoked vestibulodynia is partial, the duration of provoked vestibulodynia will be calculated as follow: 1) If only day is missing, only month and year will be used in calculation. 2) If month is missing, only year will be used in calculation. 3) No imputation should be done at the data level.

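### SAP 3.9.2 treats missing information non-conservatively in the related, severity and AESI counts: unassessable AESI candidates are dropped, and missing causality is never counted as related

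*SAP*

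**What the plan says.** SAP 3.9.2 has three relevant rules.

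- **Single event.** "If the intensity or causality is missing for a TEAE, it will be considered as missing in the summary tables". The blank is shown as its own category and is not recoded.
- **Several events.** "In the event of multiple TEAE being reported by the same subject within the same SOC/PT", one value is chosen. For intensity it is "the maximum intensity (severe > moderate > mild > missing". For causality, "the most serious causality (related > not related > missing) will be chosen".
- **AESI candidates.** Events found by the preferred-term lists and the hypersensitivity SMQ are reviewed medically by the sponsor before database lock and unblinding. Grounds for setting a candidate aside are another explanation for the event, a local rather than distant effect, implausible timing, "or due to insufficient information/evidence to make an assessment". The SAP continues: "In the summary data tabulations and listings, only the final list of AESIs confirmed by the sponsor" are taken into account.

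The overall AE table in 3.9.2 has rows for related TEAEs, related TEAEs by maximum intensity, and related SAEs. No row for missing causality is named.

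For dates, SAP 3.10.2 takes another line: "The most conservative approach will be systematically considered". An event with a missing or incomplete onset date is treated as treatment-emergent unless other data point the other way.

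**The concern.** Protocol 8.1.4 and SAP 3.9.2 define an AESI by whether a causal link to Dysport is reasonably possible, whatever causality the investigator recorded. Lack of information does not rule that possibility out, yet the SAP lets it remove the event. Protocol 8.1.4 names alternative aetiology, injection location and timing as review variables. The list is open-ended, but insufficient information is not among the grounds it names, and SAP section 5 does not record the addition as a change from the protocol.

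The causality ranking has a related problem. Protocol 8.1.2.2 reserves 'not related' for reports that contain enough information to exclude a causal link. A blank does not meet that test, but beside a 'not related' event it is shown under that label.

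Safety is the Stage 1 primary objective, and the dose groups are small enough that one subject visibly moves a percentage. A reader of the AESI table cannot tell whether zero means that no candidates were found or that those found could not be assessed.

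**Working it through.** The plan gives no figure to reproduce here, so the check is of the rules' logic and then of the weight of one subject.

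**1. Causality patterns.** Take one subject and one SOC/PT with one or two events. Four patterns contain a missing causality. The bracketed figure is the contribution to the related count.

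| Pattern | SAP rule | Missing ranked above 'not related' | Missing counted as related |
|---|---|---|---|
| missing | missing (0) | missing (0) | related (1) |
| not related + missing | not related (0) | missing (0) | related (1) |
| missing + missing | missing (0) | missing (0) | related (1) |
| related + missing | related (1) | related (1) | related (1) |

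Three results follow.

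- The SAP ranking hides the blank behind a milder label in one pattern only, 'not related' plus missing. Re-ranking restores the label but leaves the related count unchanged.
- In three of the four patterns the related count is 0 under the SAP and 1 if missing is taken as related. Only that second rule changes the count.
- The subject counts once as having a TEAE in every pattern, so the any-TEAE total does not move.

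Intensity works the same way: mild plus missing is shown as mild.

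**2. AESI candidates.** Set the rules side by side. The definition needs a reasonably possible link, the review may reject for insufficient information, and the AESI outputs hold confirmed events only. An unassessable candidate therefore appears in neither the AESI table nor the AESI listing. It stays in the general TEAE tables and the all-AE listing. The flags named for the AE listings are TEAE, pre-treatment and clinically significant; none marks an AESI candidate or gives the reason for rejection.

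**3. Weight of one subject.** Planned Dysport numbers come from Protocol 3.1.1 and 3.7.2.1, for the six cohorts that SAP 1.3.5 says will be analysed.

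| Dose | Planned on Dysport | One subject |
|---|---|---|
| 100 U | 8 | 1/8 = 12.5 points |
| 300 U | 8 | 1/8 = 12.5 points |
| 400 U | 8 + 6 = 14 | 1/14 = 7.1 points |
| 500 U | 8 + 8 = 16 | 1/16 = 6.25 points |
| All Dysport | 8 + 8 + 14 + 16 = 46 | 1/46 = 2.2 points |

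These are weights, not estimates of bias. A percentage moves only if the subject has no other qualifying event.

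**The case against.** The strongest reply is that the SAP declines to impute rather than imputing favourably. A lone blank stays visible as missing in the by-causality and by-intensity tables, the ranking bites in one narrow pattern, and the conservative promise in 3.10.2 is made for dates only. Blanks should also be few: Protocol 8.1.5 requires a causality assessment for every AE, and 8.1.6 has the sponsor request it when an SAE report lacks it. AESI review precedes unblinding and does not depend on investigator causality, so a blank causality alone cannot remove an AESI.

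Most of this stands, and it limits the point. It does not answer the AESI rule, which turns on insufficient information of any kind and leaves no trace of the rejection. Review before unblinding limits steering by arm in cycle 1, but Dysport is open-label in cycles 2 to 4, and blinding does not correct an undercount.

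Three stronger readings are tempting, and the documents do not support them.

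- **That incomplete reporting can only lower the safety counts.** The onset-date rule in SAP 3.10.2 can add TEAEs, and any-TEAE and any-SAE totals do not depend on causality or intensity.
- **That rejected AESI candidates vanish from the report.** They remain in the TEAE tables and the AE listing. What is lost is their status as candidates and the reason for rejection.
- **That clinically significant AEs or DLEs are undercounted by the ranking.** Protocol 3.1.1.1 defines these event by event, the DRC reviews them, and SAP 3.9.2 flags and lists clinically significant events separately.

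**Conclusion.** The point holds for three families of counts: events related to the study drug, events by intensity, and AESIs. For these, a missing value or an unassessable candidate can lower the reported count and cannot raise it, and the SAP plans no table showing the other extreme. The AESI rule is the more serious part, because it departs from the definition's own threshold and cannot be traced in the outputs. The ranking is a smaller matter of labelling.

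The actual effect cannot be calculated, since neither document gives an expected rate of missing causality, missing intensity or unassessable candidates. It may be nil. The per-subject weights assume the planned numbers per dose; actual numbers may differ through replacement or an extra subject accepted into a cohort. The change is worth making because it is cheap and the primary objective is safety.

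**What to change.** 1. Keep search-identified candidates with insufficient information in the AESI table as a separate 'not assessable' row, so that the confirmed count is unchanged but the uncertainty is visible. List every search-identified TEAE with the sponsor's decision and reason.
2. In the SOC/PT tables, rank missing above 'not related' and above 'mild'. A blank beside a moderate event would still be shown as moderate.
3. In the overall AE table, add a footnote or sensitivity row giving related TEAEs and related SAEs with missing causality counted as related. Leave the raw blank in the listings.

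Missing intensity should not be recoded as severe in the main tables. An event lacking both values would then be tabulated as drug-related and severe, which is one of the clinically significant AE categories, and could conflict with the separate listing.

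The cost is SAP wording, one AESI row, one listing and one footnote or row. The downside is that the safety figures may look slightly less favourable.
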